Study Protocol and Statistical Analysis Plan

Title: Impact of muscle temperature on muscle growth and breakdown: Cooling during resistance training

NCT05302791

Unique Protocol ID 0072-22-FB

Date: 19 Apr 2022

Abstract

The purpose of this study is to examine the effect of human skeletal muscle temperature during resistance exercise on myogenic and proteolytic signaling. Study participants will be eligible if they are male or female aged 19-45, recreationally active, and considered 'low risk' for activity participation. Participants will perform bilateral resistance exercise bouts at an intensity that should stimulate a muscle growth response in the Vastus Lateralis. During the resistance exercise, the participants will receive a cold (10°C) intervention on the experimental limb, while receiving a neutral temperature intervention (22°C) on the control limb. Skin and intramuscular temperatures, local blood flow, and skeletal muscle biopsies will be collected from each leg pre-, immediately post, and following the 3-hour recovery to evaluate myogenic and proteolytic related gene and protein expression.

Purpose and Rationale

To test the hypotheses that skeletal muscle cooling will inhibit the cell signaling response associated with muscle growth and that skeletal muscle cooling will inhibit the resistance exercise induced skeletal muscle growth response.

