The investigator's laboratory has recently published a proof-of-concept study that investigated the human myogenic and proteolytic transcriptional response to resistance exercise when one leg was heated, and the other leg was cooled (5). The results from this study indicate that the exercise-induced response was different between the heated and cooled leg, in favor of the heated leg. With this initial study design, it cannot be determined if heating produced a favorable response or if cooling produced an inhibitory response. Furthermore, it is unsure the impact of temperature independent of exercise. The currently proposed studies will allow these questions to be answered with greater mechanistic resolution. There are few human studies that have addressed this issue. However, these studies do not lead to the same conclusions. No statistical benefit in muscle hypertrophy or strength was observed with local muscle heating after 12 weeks of resistance training (Stadnyk 2018). It should be noted that the difference in muscle temperature between experimental and control conditions was only ~1°C. Using a similar design Goto et al (2007) demonstrated an increase in muscle hypertrophy and strength, although this observation may be due the non-dominant limb serving as the experimental (heating) condition. Unfortunately, these previous studies did not measure any molecular aspects that could have allowed more clear interpretation of the data and assessment of the protocols used nor did they investigate the impact of heat alone. To our knowledge only one study has investigated the resistance exercise mTOR signaling response in humans. This study indicates that heat enhances mTOR signaling after resistance exercise in human skeletal muscle (Kakigi 2011). Unfortunately, this study used

microwave therapy to increase the muscle temperature much quicker and greater than typical external heat modalities. The issue with the use of microwave therapy is that this modality may have other non-thermal effects on cell membrane integrity (Rougier 2014) which in turn could activate the mTOR pathway. More clear rationale for the use of heat to enhance muscle growth comes from rodent and culture models. Heat stress appears to activate the Akt/mTOR pathway (Yoshihara, 2013) and attenuate muscle atrophy (Naito, 2000) in rats.

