Participants will then perform a Repetition Max Test for bilateral seated leg press and seated leg extension using the following protocol on isotonic exercise machines at a weight designed to create failure between 8 and 12 repetitions. Following a short warm-up on a cycle ergometer, the participants proceed with a bilateral leg press warm-up consisting of one set of ten repetitions at a self-determined light load, then one set of 5 repetition at a self- determined moderate load, and one set of 1 repetition at a predicted 12 rep maximum as predicted in relation to their Fat Free Mass. During the warm-up participants will be coached on form and observed for their ability to complete the repetition max test. Weight for the test will be altered to suit the participants' ability to complete approximately 12 repetitions. Once the desired weight is determined,

participants will be asked to complete as many repetitions as possible until the participant can no longer complete a repetition using a full range of motion.

An identical testing protocol is then performed for the leg extension. This data will be used to estimate a 12RM workload, that would be appropriate for hypertrophic growth using the Watham equation (46).

Experimental Visit (~6.5-8 hours):

Participants will be instructed to arrive to the lab having fasted overnight, and they will be asked to avoid strenuous activity, alcohol consumption, tobacco use, and drug use for the 24-hour period leading up to experimental trial.

Participants will complete the following experimental protocol briefly described: consume a small meal, a pre-exercise muscle biopsy, precool for 30 minutes, complete the exercise intervention, immediately post-exercise biopsy, 4-hour recovery with cooling, and post-recovery biopsy. At three time points (pre-exercise, immediately post-exercise, and post-4-hour recovery), skin temperature, muscle temperature, blood flow, and muscle tissue biopsies will be taken.

Details are as followed:

Meal

When participants arrive, a consistent meal will be provided to standardize dietary intake. Food choices will be given to participants to create a meal between 700-800 calories, containing approximately 25-35 g of protein, 75-85 g of carbohydrates, and 35-45 g of fat. These foods will be made-up of commercially available pre-packaged foods. They will have approximately 30 minutes to consume their meal.

Cooling protocol

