Participants will have Game Ready Med 4 elite (<https://gameready.com/med-4-elite-contrast-therapy-unit/>.) thigh wraps around each thigh. This system circulates cooled liquid through a wrap specifically fitted for different body segments. One thigh will be cooled while the other thigh will be wrapped with the cuff, but not have any liquid circulating through it. These wraps do provide slight compression and thus it is important to apply the wraps to both legs. Each leg is assigned to either cold experimental group or control, will be randomized and counter-balanced between participants. The liquid temperature circulating through the thermal wraps will be set to 10°C. This temperature has been shown in investigator's previous works to not injure the participants' skin. The thermal wraps will be worn during a 30-minute cool down period prior to the exercise bout, during the exercise intervention, and during a 4-hour recovery period.

Exercise Intervention

The participants will complete an intervention designed to stimulate the muscle growth signaling pathway (hypertrophy) in the Vastus Lateralis (outer thigh), via bilateral seated leg press and bilateral seated leg extension on isotonic exercise machines. Participants will perform four sets of bilateral leg press exercises at the weight determined to be their 12 RM from the repetition max test. This should allow completion to failure of 8-12 repetitions. So, if more than 12 reps are able to be completed, weight will be added to the resistance for the subsequent sets. Conversely, if less than 8 reps lead to failure, the weight should be reduced for the subsequent sets. Constant dialogue with participants will give investigators the ability to monitor set weights to maximize a hypertrophic response. Participants will be allowed 2 minutes of rest between each set. Upon

completion of 4 sets, the participants will be given 5 minutes of rest prior to repeating this protocol for bilateral leg extensions.

Biopsies

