A total of 6 muscle biopsies (1 per leg) will be obtained from the vastus lateralis (outer thigh) muscle. One from each leg for each of the three collection time-points, pre-exercise, immediately post-exercise, and post-4-hour recovery. The PI will conduct these biopsies, having successfully completed over 600 biopsies without any adverse events. Briefly, the area above the vastus lateralis muscle belly will be shaved and cleaned with alcohol. 1% xylocaine is then injected under the skin with a 25 ga hypodermic needle. The Xylocaine will be ordered with a prescription provided by the participating physician.

The area is then further disinfected with betadine, and a sterile fenestrated drape is placed over the biopsy site. Using sterile techniques, a small incision is made through the skin (~5mm) and the Bergstrom biopsy needle is inserted through the incision into the belly of the muscle. The Bergstrom needle then takes a small clip of muscle (~50mg) and is removed from the muscle and stored in a chemical stabilizer at -30°C. Slight pressure is held over the incision for approximately 2 minutes and is then closed using steri-strips and a band-aid with antibiotic ointment. The leg is further dressed with a compression bandage.

Participants are all instructed how to care for the wound and given the investigators contact information in case they have further questions.

Intramuscular Temperature

Using the incision from the muscle biopsy, a hypodermic (~26ga) thermocouple (Physitemp Instruments LLC, Clifton, NJ) that is smaller than the needle used to inject the xylocaine will be inserted into the belly of the muscle to measure intramuscular temperature. The thermocouple readings stabilize in approximately 3 seconds and the thermocouple is then removed. Under normal circumstances, the sensation of this temperature reading is similar to an intramuscular injection. However, with the use of the biopsy incision as the insertion point there is very little sensation associated with this measure. Recordings for intramuscular temperature will be collected during the biopsy process following the 4-hour temperature intervention.

Skin Temperature

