Skin Temperature will be measured on the surface of each thigh using a skin thermistor (Physitemp Instruments LLC, Clifton, NJ), infrared digital thermometer, and/or using an infrared thermal camera. Measurements will be taken at the same time as the intramuscular. The thermistor is simply placed on the skin for approximately 3 seconds and is then recorded. The infrared digital thermometer can measure and record surface temperature from a distance of 12 inches. The infrared thermal camera can measure and record surface temperatures for a field of multiple surfaces.

Gene Expression Analysis

The muscle tissue collected will be processed and analyzed for transcriptional changes of genes associated with muscle growth and breakdown. Muscle mRNA content will be evaluated using real-time reverse transcription quantitative polymerase chain reaction (real- time RT-qPCR). Quantification of mRNA for genes of interest will be computed using the $2-\Delta\Delta CT$ method and compared to stable reference genes. Probes and Primers that will target the specific gene sequences will be attained from Integrated DNA Technologies (IDT, Coralville, IA).

Protein Expression Analysis

The muscle tissue collected will be processed and analyzed for proteins associated with muscle growth and breakdown. Standard western blotting protocols will be optimized and used to evaluate the muscle growth signaling cascade, using antibodies specific to the proteins of interest and normalized to total protein.

Statistical Analysis

Recruitment

Previous exercise research suggests that the difference in response of matched pairs is normally distributed with a standard deviation of 0.86. If the true difference of the mean response of matched pairs is 0.75, we will need to complete 12 experimental trials for each condition to be able to reject the null hypothesis that this response difference is zero with a power of 0.8. The Type I error probability associated with this test of the null hypothesis is 0.05.

Interventions

A repeated measures two-way ANOVA will be used for the dependent variables. If the F-ratio values are found to be significant then a Fishers protected Least Significant Difference post hoc will be performed to evaluate where the significance occurs. The probability of type I error must be less than 5% in order to be considered significant ($p < 0.05$). All Statistical data will be analyzed using the Statistical Package for Social Sciences software (SPSS 24.0)

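### mRNA is quantified as fold change and, read literally, analysed on that scale; ΔCT with contrast-specific errors would avoid missing a cooling effect at the less induced biopsy

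*Combined protocol and SAP*

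**What the plan says.** All references are to the combined protocol and SAP.

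- **Quantity.** Gene Expression Analysis: "Quantification of mRNA for genes of interest will be computed using the" 2^-ΔΔCT method, relative to stable reference genes. The reference genes are the normaliser (the first Δ). The calibrator sample for the second Δ is not named.
- **Model.** Statistical Analysis, Interventions: "A repeated measures two-way ANOVA will be used for the dependent variables". The factors are not named; the design implies leg (2) by time (3).
- **Post hoc tests.** Same section: "If the F-ratio values are found to be significant then a Fishers protected Least Significant Difference post hoc will be performed". It does not say whether the leg, time or leg × time F opens the tests, or whether the LSD uses the pooled ANOVA error or an error specific to each contrast.
- **Layout.** Biopsies: "One from each leg for each of the three collection time-points, pre-exercise, immediately post-exercise, and post-4-hour recovery".
- **Order and allocation.** Experimental Visit lists "a pre-exercise muscle biopsy, precool for 30 minutes", so the first biopsy precedes any cooling. Cooling protocol: "Each leg is assigned to either cold experimental group or control, will be randomized and counter-balanced between participants".
- **Aim.** Purpose and Rationale includes the hypothesis that "skeletal muscle cooling will inhibit the resistance exercise induced skeletal muscle growth response".

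**The concern.** Fold change is the only mRNA quantity named, and no log or ΔCT analysis scale is mentioned. If noise is roughly constant in CT cycles, its SD in fold-change units is proportional to the mean. If each leg's own pre-exercise sample is the calibrator, every pre value is exactly 1 and has no variance at all. An error term shared by three such biopsies is then too small where the gene is most expressed and too large where it is less expressed.

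Two post-exercise biopsies per leg are taken to see whether, and when, cooling alters the response. An analysis dominated by one of them can miss an effect at the other. With a pooled error it can also attribute the effect to the wrong time.

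**Working it through.** **1. The plan's own figure.** Recruitment gives difference 0.75, SD of paired differences 0.86, alpha 0.05, power 0.8, n = 12. Noncentrality = (0.75/0.86) × √12 = 3.02. A two-sided paired t test on 11 df has power 78.5%, and 13 pairs are needed to pass 80%. The stated 12 is reproduced closely enough. The units of 0.75 and 0.86 are not given, so they cannot be tied to either mRNA scale.

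**2. Assumptions.** Only n = 12 and the 2 × 3 layout come from the documents. Assumed: log2 SD 0.6 per biopsy within a participant, participant SD 0.5, induction 1.7-fold (immediately post) then 4-fold (post-recovery), and a cooling effect of −0.75 log2 units. The correlation between pre- and post-exercise leg differences is set at 0, 0.3 and 0.5. The calibrator is either the own-leg pre sample or common to all samples.

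**3. Why one error term does not fit.** On the log2 scale the SD is 0.6 at every biopsy. On fold change the SD is proportional to the mean, so the 4-fold biopsy has (4/1.7)² = 5.5 times the variance of the 1.7-fold biopsy. The effect multiplies expression by 2^-0.75 = 0.595, a fall of 0.405. That is 1.7 × 0.405 = 0.69 fold units at one biopsy and 4 × 0.405 = 1.62 at the other.

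With a common calibrator, correlation 0 and no leg effect, leg-difference variances are in the ratio 1 : 2.89 : 16, and the pooled error estimates their mean, 19.89/3 = 6.63. The pooled standard error is √(6.63/16) = 0.64 of its correct value post-recovery and √(6.63/2.89) = 1.51 times it immediately post.

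**4. Simulation (20,000 trials per setting).** Triplets are correlations 0/0.3/0.5; for fold change, own-leg calibrator first, then common. The null ranges for fold change cover SD 0.4–0.8.

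| | Fold change, pooled error, leg × time gate | Fold change, contrast-specific error, leg × time gate | ΔCT, contrast-specific error, leg or leg × time gate |
|---|---|---|---|
| True null: immediately post | 0.2–0.6% | 0.4–1.0% | about 5% or less |
| True null: post-recovery | 5.9–7.3% | 3.1–4.7% | about 5% or less |
| Effect immediately post only: power there | 0.04/0.07/0.11; 0.09/0.10/0.12 | 0.06/0.10/0.15; 0.14/0.14/0.16 | 0.66/0.70/0.75 |
| Same: false positives post-recovery | 11–14% | 3.6–4.8% | about 5% or less |
| Effect at both: power immediately post | 0.18/0.31/0.49; 0.26/0.38/0.48 | 0.28/0.45/0.65; 0.48/0.56/0.61 | 0.78/0.77/0.78 |
| Effect at both: power post-recovery | 0.48/0.65/0.80; 0.65/0.75/0.82 | 0.42/0.59/0.75 (own-leg) | 0.78/0.77/0.78 |
| Effect post-recovery only: power there | 0.57/0.74/0.88; 0.73/0.82/0.88 | – | 0.66/0.70/0.75 |

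**5. Isolating the scale.** The last column differs from the others in its gate as well. With the gate (leg or leg × time) and the contrast-specific error held the same, power for an immediately-post-only effect is 0.10–0.22 on fold change and 0.66–0.75 on ΔCT. That contrast is due to scale.

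**6. Sensitivity.** Reversing the order of induction mirrors the fold-change results. At log2 SD 0.3, power for an immediately-post-only effect under pooled fold change rises to 0.34/0.54/0.76 and 0.55/0.65/0.73. On ΔCT, induction adds the same constant to both legs, so those results do not depend on it.

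**The case against.** **The plan does not forbid ΔCT.** True. An analyst might log-transform as a matter of course. Nothing in the text says so, and the point rests on the literal reading.

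**The error-rate imbalance needs a pooled error, which is not stated.** This stands. Pooled error is the usual meaning of Fisher's LSD, but contrast-specific errors on fold change hold each biopsy at about 4–5% or below.

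**It also needs unequal induction.** This stands too. With equal 2-fold induction the pooled rates under the leg × time gate are equal, at about 3% each. The documents give no induction profile.

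**A reader might infer false-positive rates of 20–29%.** That happens at the more induced biopsy if a significant time F opens pooled-error leg comparisons on fold change. The wording does not strictly exclude this, but it is a strained reading: the post hoc tests are meant to locate the significance found, and a time effect does not lead to a comparison of legs. With contrast-specific error the rate would be 4.1–4.8% even then.

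**Power comparisons depend on the gate.** With a leg or leg × time gate and the effect at both biopsies, pooled fold change reaches 0.58/0.74/0.87 (own-leg) and 0.87/0.85/0.86 (common) post-recovery, though it rejects a true null there in 7.5–8.8% of trials. Nor does scale alone help much at the more induced biopsy: with the leg × time gate and contrast-specific error, ΔCT gives 0.47/0.59/0.69 against 0.42/0.59/0.75 for own-leg fold change. The gain from scale is at the less induced biopsy.

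**A reader might infer that the ANOVA must be replaced** by regression on the pre-exercise leg difference with Holm over the two biopsies. The figures do not show that. With the effect at both biopsies the regression gives 0.70/0.74/0.82, against 0.78/0.77/0.78 for the ΔCT ANOVA with protected LSD.

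**Conclusion.** The concern holds in a limited form. Four choices are unstated: calibrator, scale, gating F and LSD error term. The literal choice of scale is a poor one for this design. Under the assumptions above, fold change misses most cooling effects confined to the less induced biopsy (power 0.04–0.12 pooled, 0.06–0.16 contrast-specific, 0.10–0.22 with the wider gate), where ΔCT finds 0.66–0.75.

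Inflated and unequal false positives are a conditional second harm: they need both pooled error and unequal induction. The sizes depend on an SD, induction profile and correlation that the documents do not supply, and they shrink as the SD falls; the direction follows from variance rising with the mean. This should be settled before the mRNA data are analysed. It does not call the planned 12 participants into question, and these calculations concern mRNA only.

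**What to change.** In Statistical Analysis, Interventions, state for mRNA that:

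1. the analysis variable is ΔCT (log2 scale), with the calibrator named for reporting;
2. the leg × time ANOVA and protected LSD are kept, and a significant leg or leg × time F, but not a time F alone, opens the leg comparisons;
3. the cold-minus-control difference at each post-exercise biopsy is tested with its own paired error (11 df). Pooled error would not be safe on ΔCT either: if ΔCT variance differed by time (SD 1.5 times larger post-recovery), pooled LSD would give 2.2% against 11.6%;
4. results are back-transformed to fold change with confidence intervals.

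Because the first biopsy precedes cooling and legs are randomized, these post-exercise leg differences estimate the cooling effect directly.

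**Cost.** SAP wording and different SPSS commands; no new data. With an effect only at the more induced biopsy, power (0.66/0.70/0.75) is below pooled fold change with the leg × time gate in five of six settings. This is partly because that test exceeds 5% there. With its critical value raised to give 5%, it has 0.45/0.61/0.77 and 0.70/0.76/0.78, still higher in four of six, by 2 to 6 points.

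**Optional.** The pre-exercise leg difference may be added as a covariate, and Holm applied over the two biopsies, if chosen before analysis. The covariate helps only above a correlation of about 0.33. The laboratory's earlier study of the "human myogenic and proteolytic transcriptional response to resistance exercise when one leg was heated, and the other leg was cooled" could supply that correlation and the SD, if it has pre-exercise samples from both legs.

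### The pre-cooling biopsy in each leg is not planned as a baseline covariate, and on the natural leg-by-time reading it enters the ANOVA as an outcome level: a cheap improvement is available

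*Combined protocol and SAP*

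**What the plan says.** Under Statistical Analysis, Interventions, the whole model statement is that "A repeated measures two-way ANOVA will be used for the dependent variables", with a Fisher protected LSD step after a significant F. The factors, their levels, the F that tests cooling and the role of the pre-exercise value are not stated. No covariate or change score is mentioned.

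The Experimental Visit section gives the order of events as "consume a small meal, a pre-exercise muscle biopsy, precool for 30 minutes, complete the exercise intervention". The first biopsy therefore precedes any cooling. Under Cooling protocol, legs are randomized to cold or control and counter-balanced across participants. Under Biopsies, both legs are sampled at three times, one before cooling and two after it starts.

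Under Statistical Analysis, Recruitment, the sample size rests on a single matched-pair comparison: "the difference in response of matched pairs is normally distributed with a standard deviation of 0.86", and "If the true difference of the mean response of matched pairs is 0.75", then "we will need to complete 12 experimental trials for each condition".

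**The concern.** Legs are randomized and the first biopsy is taken before cooling, so a leg difference at that time is chance. It carries no treatment effect but may predict the later leg difference. With two legs and three times, the natural two-way layout is leg by time, and the pre-exercise value then becomes one of three outcome levels. Three consequences follow on that reading:

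- The leg main effect averages in a time at which cooling cannot have acted.
- The leg-by-time F uses the pre-exercise value by full subtraction, as a change score does, and spreads the test over 2 degrees of freedom.
- An LSD comparison of legs at a post-exercise time would not use the pre-exercise value, and it is reached only after a significant F.

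None of these is the matched-pair test on which the 12 participants were sized. With 12 pairs, the precision of the leg contrast matters a good deal.

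**Working it through.** **Inputs from the documents (Recruitment).** Difference 0.75; SD of the paired difference 0.86; 12 pairs; "with a power of 0.8"; "The Type I error probability associated with this test of the null hypothesis is 0.05". Sidedness is not stated. It is taken as two-sided because the aim is to "reject the null hypothesis that this response difference is zero".

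**Assumptions not in the documents.** SD 0.86 for the leg difference at each of the three times; a common correlation r among the three leg differences, shown from 0 to 0.7; normality; no leg difference before cooling.

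**The plan's own figure.** Normal approximation: n = ((1.960 + 0.842) × 0.86 / 0.75)² = 10.3, so 11 pairs. Exact paired t, two-sided: power 0.785 at 12 and 0.823 at 13. The stated 12 is reproduced, at slightly under 0.80.

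**Dilution of the leg main effect (three-time reading).**
- Equal effect at both post-exercise times: (0 + 0.75 + 0.75) / 3 = 0.50, two thirds of 0.75.
- Effect at one time only: (0 + 0 + 0.75) / 3 = 0.25, one third.

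**Variance of the estimated cooling effect at one post-exercise time, relative to the unadjusted paired comparison.**
- Change from pre-exercise: 2(1 − r).
- Unadjusted post-exercise difference: 1.
- Baseline-adjusted: (1 − r²) × (1 + 1/(n − 3)). At n = 12 the second factor is 1 + 1/9 = 1.11, the price of estimating the slope.

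| r | Change | Unadjusted | Adjusted |
|---|---|---|---|
| 0 | 2.00 | 1 | 1.11 |
| 0.3 | 1.40 | 1 | 1.01 |
| 0.5 | 1.00 | 1 | 0.83 |
| 0.7 | 0.60 | 1 | 0.57 |

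Adjusted and unadjusted break even where 1 − r² = 0.9, that is r of about 0.32.

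**Power by simulation, n = 12, effect 0.75 at the named time only.** The adjusted test is the intercept of the post-exercise leg difference regressed on the pre-exercise leg difference (10 df). The LSD step is taken as a paired t at that time, counted only if the gate opens. Results are from 40,000 trials per setting and are good to about 0.01.

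| r | Adjusted | LSD, interaction F as gate | LSD, either F as gate | Leg-by-time F alone | Ungated unadjusted paired t |
|---|---|---|---|---|---|
| 0 | 0.74 | 0.51 | 0.65 | 0.53 | 0.79 |
| 0.3 | 0.78 | 0.62 | 0.69 | 0.69 | 0.79 |
| 0.5 | 0.85 | 0.70 | 0.73 | 0.84 | 0.79 |
| 0.7 | 0.95 | 0.77 | 0.78 | 0.97 | 0.79 |

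**Averaging both post-exercise times instead.** With an effect at one time only, the adjusted test of the post-exercise mean has power 0.46/0.42/0.46/0.58 at r = 0/0.3/0.5/0.7. This is well below the single-time test, so the two analyses are not interchangeable.

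**If 0.86 is already the SD of a change.** The post-exercise SD is then 0.86 / √(2(1 − r)), and the residual SD after adjustment is 0.86 × √((1 + r)/2). With the same slope penalty, adjusted power is about 0.95/0.89/0.85/0.80 at r = 0/0.3/0.5/0.7, against 0.785 for the change test. The figures move, but adjustment remains at least as good as the change score.

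**The case against.** Three stronger readings are tempting, and the documents support none of them.

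- **That the plan enters the pre-exercise biopsy as an outcome level.** The plan names no factors or levels. This is the natural reading, not a stated fact. The same holds for what the LSD step would compare.
- **That the planned analysis dilutes the cooling effect.** Only the leg main effect is diluted. The leg-by-time F is the usual test of whether cooling alters a response to exercise. It already uses the pre-exercise value and is not diluted. At r = 0.7 it is slightly ahead of the adjusted single-time test (0.97 v 0.95).
- **That the covariate lifts power from about 0.70 to 0.93.** At r = 0.3, with equal effects at both post-exercise times, the main effect has 0.71, the interaction 0.70 and the adjusted post-exercise mean 0.93. But the unadjusted post-exercise mean also has 0.93. At r = 0 and 0.5 the unadjusted mean has 0.97 and 0.89, against 0.95 and 0.95 adjusted. Most of that gap comes from averaging two times, not from the covariate.

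Two further objections stand. The documents do not give r, and adjustment costs precision when r is low. Also, Gene Expression Analysis does not name the 2-ΔΔCT calibrator. If each leg is calibrated to its own pre-exercise sample, the pre-exercise mRNA value is constant and cannot serve as a covariate.

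The objections do not remove the point. The plan provides no free-standing post-exercise test, since the LSD step follows only a significant F. Against that gated route, the adjusted test has higher power at every r shown when the effect is at the named time only.

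**Conclusion.** The point holds as a cheap improvement, with moderate confidence. A pre-treatment value is already collected in each randomized leg, and the plan does not use it as a covariate. For an effect at the named time only, adjustment gains 18 to 23 points over the LSD comparison gated by the interaction F (0.74 − 0.51 = 0.23 at r = 0; 0.95 − 0.77 = 0.18 at r = 0.7). It gains 9 to 17 points if either F opens the gate (0.74 − 0.65 = 0.09; 0.95 − 0.78 = 0.17).

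It is not better everywhere. At r of about 0.3 or less it is up to 5 points below an ungated unadjusted paired test (0.74 v 0.79 at r = 0). At r = 0 with both post-exercise times affected, it is below the either-F route (0.74 v 0.77).

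These sizes rest on the three-time reading, SD 0.86 at each time, effect 0.75 and an assumed common r. A reader should not infer that the planned ANOVA is invalid: its Type I error was 0.05 for both F tests in simulation under these assumptions. The issues are efficiency and an unnamed target.

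**What to change.** In Statistical Analysis, Interventions:

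1. Name the factors, and name the post-exercise time at which cooling is tested. If both times are tested, add a multiplicity rule. The power figures above are for one time at 0.05.
2. For each marker, compute the within-participant leg difference (control minus cooled) at that time, regress it on the same participant's pre-exercise leg difference, and test the intercept as the cooling effect. Leave the pre-exercise difference uncentred. Its expected value is zero under randomization, and centring at the sample mean would turn the intercept back into the unadjusted mean difference.
3. Keep the three-time ANOVA to describe the time course. Do not present a model averaged over both post-exercise times as equivalent to step 2.
4. For mRNA, analyse ΔCT or use a common calibrator, not each leg's own pre-exercise sample, so that the covariate has variance.
5. State in Recruitment whether 0.86 is the SD of a post-exercise leg difference or of a change.

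The cost is SAP wording and a few lines of SPSS syntax. Statistically it is one error degree of freedom plus about 11% extra variance from estimating the slope, which is recovered once r exceeds about 0.3. No visit, biopsy or procedure changes.
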